#### 9.3.2 Analysis of the Secondary Efficacy Variables

Absolute change from period baseline in serum levels of immunoreactive trypsinogen at 8 weeks of treatment will be summarized using summary statistics only. In addition a data listing of IRT data will be produced. As two different IRT assays were used these data will be analyzed in two separate subsets classified by their assay platforms and analyzed by period baseline.

Absolute change from baseline in fecal elastase-1 at 8 weeks of treatment will be summarized using summary statistics only. In addition a data listing will be produced.

Absolute change from baseline in weight at 8 weeks of treatment will be summarized using summary statistics only. In addition a data listing will be produced.

Absolute change from baseline in body mass index (BMI) at 8 weeks of treatment will be summarized using summary statistics only. In addition a data listing will be produced.

[REDACTED]

## 9.4 Safety Analysis

The safety profile of study drug will be assessed in terms of the following safety and tolerability data from Part 1:

- Adverse events
- Clinical laboratory values (hematology, serum chemistry, liver function tests, coagulation studies, and urinalysis)
- Vital signs
- Ophthalmology

Safety endpoints will be analyzed based on the Safety Set (for each applicable treatment period). Only descriptive analysis of safety will be performed and no statistical testing will be performed.

### 9.4.1 Adverse Events

For analysis purposes, adverse events will be classified as pre-treatment emergent, TEAE, or post-treatment emergent. Adverse events which start (or increase in severity) during the period from the signing of informed consent up to, but not including, the first dose of study drug will be considered pre-treatment. Adverse events which start (or increase in severity) during the period from the first dose of study drug through completion of the Follow-up Visit will be considered TEAE. Adverse events which start (or increase in severity) after the completion of the Follow-up Visit will be considered post-treatment adverse events.

If an adverse event started (or increased in severity) during a specific treatment period, this adverse event will be attributed to the study drug the subject is receiving during this Treatment Period. Adverse events that started (or increased in severity) during the Washout Period and within 28 days of the last dose of treatment period 1 will be attributed to the treatment received in Treatment Period 1. Please see Section 9.1 for details.

For determining whether the AEs with missing or partially missing dates are treatment-emergent, please refer to Appendix D for rules. Please note that no imputation will be displayed in the listing outputs.

Adverse event summary tables will be presented for TEAE only and will include the following:

All TEAEs,

Related (defined as possibly related or related) TEAEs,

TEAEs leading to treatment discontinuation,

Serious TEAEs,

TEAEs by severity,

TEAEs by relationship.

Summaries will be presented by MedDRA system organ class and preferred term using frequency counts and percentages (i.e., number and percentage of subjects with an event). Subjects with multiple occurrences of the same adverse event or a continuing adverse event will be counted once, and only the maximum severity level will be presented in the severity summaries, and the worst/highest relationship level in the relationship summaries. In addition,

listing containing individual subject adverse event data for all deaths and other serious and significant adverse events will be provided, separately. All adverse events including Pre- and Post-treatment adverse events will be presented in individual subject data listings.

Imputation rules for missing or partial AE dates are presented in Appendix D.

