#### **8.1.3 Part 1: Washout Period (8 Weeks)**

Subjects will undergo a Washout Period of 8 weeks ( $\pm 5$  days).

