#### **12.3.5.1 Adverse Events**

TEAEs, defined as AEs that developed or worsened on or after the first dose of study drug will be summarized. AEs will be attributed to study drug depending on the date of onset of the AE and the treatment that the subject is receiving at the time of onset of the AEs. If a subject discontinued treatment during a specific period, the Safety Follow-up Visit will be considered as the end date. TEAEs will hereafter be referred to as AEs. AE summary tables will include the following:

- All AEs
- Related (defined as possibly related or related) AEs
- AEs leading to study drug treatment discontinuation
- SAEs
- AEs by severity
- AEs by relationship

Summaries will be presented by MedDRA system organ class and preferred term using frequency counts and percentages. A subject with multiple occurrences of the same AE or a continuing AE will be counted only once, with the highest severity or relationship.

In addition, a listing containing individual subject AE data for all deaths and other serious and significant AEs will be provided.

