## 7. STUDY DESIGN

### 7.1 Overview of Study Design

This is a 2- part, randomized, double- blind, placebo- controlled, crossover study with a long-term open- label period. A schematic figure of the study design is presented in Appendix A.

In addition to the Screening Period (up to 4 weeks in duration), subject participation is anticipated to last approximately 148 weeks (2 Treatment Periods of 8 weeks each, Washout Period of 8 weeks, Open -label Period of 120 weeks, and Follow-up Telephone Contact approximately 4 weeks after last dose of study drug).

Subjects will be randomized 1:1 to receive 1 of 2 treatment sequences during Part 1:

- Sequence 1: ivacaftor in Treatment Period 1 → washout → placebo in Treatment Period 2
- Sequence 2: placebo in Treatment Period 1 → washout → ivacaftor in Treatment Period 2

This study includes:

- Screening Period: Day -28 through Day -1 relative to the first dose of study drug
- Part 1 Treatment Period 1 through Treatment Period 2

- Treatment Period 1: Day 1 (first dose of study drug) through Week 8
- 8-week Washout Period
- Treatment Period 2: Week 16 through Week 24
- Part 2 Open-label Period: Week 24 through Week 144 (the first dose of ivacaftor during the Open-label Period will be given after completion of assessments at the Week 24 Visit); the Week 24 Visit (Part 1) is also considered the first visit of the Open-label Period.
- Follow-up Telephone Contact (4 weeks [ $\pm 7$  days] after the last dose of study drug)

Subjects who prematurely discontinue study drug treatment will be required to complete the Early Termination of Treatment Visit, which is to be scheduled as soon as possible after it is decided that the subject will terminate study drug treatment. Subjects who prematurely discontinue study drug treatment will also be required to complete the Safety Follow-up Visit, approximately 4 weeks ( $\pm 7$  days) after their last dose of study drug. If the Early Termination of Treatment Visit occurs 3 weeks or later following the last dose of study drug, then the Early Termination of Treatment Visit will replace the Safety Follow-up Visit, and a separate Safety Follow-up Visit will not be required.

Subjects will continue to complete all other scheduled study visits for assessments of efficacy and other endpoints as detailed in the Schedule of Assessments. Subjects who discontinue study drug treatment during Part 1 will not be allowed to participate in Part 2 of the study.

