**Treatment Emergent (TE) Period:**

- For Treatment Period 1 of Part 1, the TE period will be from the first dose of study drug in Treatment Period 1 of Part 1 to the earliest of the following:
  - 1) 28 days after the date of subject's treatment completion during Treatment Period 1
  - 2) Safety Follow-up Visit if discontinued study early during Treatment Period 1
  - 3) 28 days after the last dose of the study drug for subjects who discontinued the study early during Treatment Period 1 and do not have a Safety Follow-up Visit
- For Treatment Period 2 of Part 1, the TE period will be from the first dose of study drug in the Treatment Period 2 of Part 1 to the earliest of the following:
  - 1) The date of treatment completion of Treatment Period 2
  - 2) Safety Follow-up Visit if discontinued study early during Treatment Period 2
  - 3) 28 days after the last dose of the study drug for subjects who discontinued the study early during Treatment Period 1 and do not have a Safety Follow-up Visit
- For Part 2, the TE period will be from the first dose of study drug in Part 2 to the earliest of the following:
  - 1) The Safety Follow-up Visit,
  - 2) 28 days after the last dose of the study drug for subjects who discontinued the study during Part 2 and do not have a Safety Follow-up Visit,

**Visit Windowing Rules:** Appendix C defines the windows for protocol-defined visits. The windows will be applied using the following rules for both scheduled and unscheduled visits. If no measurement is available within a visit window, the assessment will be considered missing for the visit. If there is more than one measurement available within the same visit window, the following rules will be used:

- For all safety parameters, if there are multiple measurements within a visit window, then 1) the record closest to the target day will be used, with the exception of the threshold analysis in which the worst record will be used; 2) if there are multiple records within the same distance of the target day, the latest record will be used; or 3) the Safety Follow-Up (SFU) visit will not be windowed; instead, the nominal visit will be used in relevant analyses.
- For all efficacy parameters, if there are multiple measurements within a visit window, the record at the scheduled visit will be used. Otherwise,
  - If there are no measurements at the scheduled visit, then the record closest to the target day will be used;

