### 9.2.5 Study Drug Exposure

Exposure summaries will be based on the Safety Set.

Duration of study drug exposure is defined as: last dose date – first dose date + 1 day, regardless of any interruption in dosing between the first and the last dose for each treatment period. The duration will be calculated for the treatment corresponding to each treatment period.

Total exposure (in patient years) and duration of study drug exposure will be summarized descriptively (number, mean, SD, SE, median, minimum, and maximum). Total exposure is defined as the sum of the subject's duration of treatment exposure and expressed in patient years. Duration of exposure will also be summarized into categories as the following:  $\geq 1$  day,  $\geq 1$  week,  $\geq 2$  weeks,  $\geq 4$  weeks,  $\geq 8$  weeks.

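### For completers, adverse events are counted over about 84 days for the Period 1 treatment and about 56 for the Period 2 treatment, and the planned tables make no adjustment for time at risk

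*SAP*

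**What the plan says.** SAP 7.1 sets two 8-week treatment periods: "Treatment Period 1: Day 1 (first dose of study drug) through Week 8" and "Treatment Period 2: Week 16 through Week 24". Between them, Protocol 8.1.3 states: "Subjects will undergo a Washout Period of 8 weeks".

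SAP 9.1 (Treatment Emergent Period) sets different ends for the two periods. For a child who completes Period 1, the window runs to 28 days after treatment completion. For a child who completes Period 2, it ends at "The date of treatment completion of Treatment Period 2". SAP 9.4.1 repeats the Period 1 rule, so that washout events starting "within 28 days of the last dose of treatment period 1 will be attributed to the treatment received in Treatment Period 1", and refers the reader back to 9.1.

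The TEAE summaries are presented "using frequency counts and percentages (i.e., number and percentage of subjects with an event". Under SAP 9.1 (Data Presentation) the columns are the ivacaftor dose groups, placebo and overall ivacaftor. SAP 9.4 says that safety endpoints use the Safety Set for each applicable treatment period and that no safety test will be done. No event rate per unit of time at risk is planned.

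Protocol 12.3.5 frames safety as ivacaftor versus placebo and names TEAE incidence as the key safety endpoint. Protocol 12.3.5.1 attributes an event by its onset date and "the treatment that the subject is receiving at the time of onset of the AEs".

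**The concern.** A percentage of subjects with an event rises with the length of observation. Here the length depends on the period in which a treatment was given, and the longer window ends with four weeks in which the child takes no study drug. An event in the four weeks after ivacaftor is stopped in Period 1 counts as an ivacaftor event; the same event after completing ivacaftor in Period 2 does not.

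Two effects on the side-by-side percentages are possible. First, off-drug events enter both columns and blur a real difference. Second, if the longer window falls more often on one treatment, a difference can appear with no drug effect. The second effect needs unequal sequence sizes or loss after Period 1. Both are possible here: enrolment was closed early (SAP 4), withdrawn children are not replaced (Protocol 9.5), and a respiratory infection or exacerbation in the four weeks before Week 16 puts entry to Period 2 under discussion (Protocol 8.1.4).

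**Working it through.** The documents print neither the window lengths in days nor any adverse event rate, so there is no planned figure to reproduce. The windows below follow from the SAP rules. The event rates, the rate ratio, the sequence splits and the loss after Period 1 are assumptions.

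**Windows for completers**

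- Period 1: 8 × 7 = 56 days on drug, plus 28 days = 84 days.
- Period 2: 56 + 0 = 56 days.
- Ratio 84/56 = 1.5. Off-drug share of the Period 1 window: 28/84 = 33%. If the Week 8 visit falls 5 days late or early, the share is 28/89 = 31% or 28/79 = 35%.
- The washout lasts 8 weeks, so the 28-day tail lies wholly inside it.

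**No drug effect: the false gap**

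Let *a* be the expected number of events per 56 days, at a constant rate. Then P56 = 1 − exp(−a) and P84 = 1 − exp(−1.5a). With n1 children in Sequence 1 and n2 in Sequence 2, all treated in both periods:

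- ivacaftor % = (n1·P84 + n2·P56)/(n1 + n2)
- placebo % = (n1·P56 + n2·P84)/(n1 + n2)
- gap = (n1 − n2)/(n1 + n2) × (P84 − P56)

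| a | P56 | P84 | P84 − P56 | gap at 5:5 | gap at 6:4 (× 0.2) | gap at 7:3 (× 0.4) |
|---|---|---|---|---|---|---|
| 0.5 | 39.3% | 52.8% | 13.4 | 0 | 2.7 | 5.4 |
| 1 | 63.2% | 77.7% | 14.5 | 0 | 2.9 | 5.8 |
| 2 | 86.5% | 95.0% | 8.6 | 0 | 1.7 | 3.4 |

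The gap is in percentage points (differences are taken before rounding). Its sign follows whichever sequence is larger.

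Loss after Period 1 matters less. Take the planned 25 children per sequence and assume that 20% of Sequence 2 never start Period 2. Ivacaftor then has 25 + 20 = 45 children, of whom 25/45 = 0.556 have the long window, against 0.500 on placebo. The gap is 0.056 × (P84 − P56), or 0.5 to 0.8 points. Equal proportional loss from both sequences gives 0.

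**Real drug effect, equal complete sequences: attenuation**

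Assume that the event rate on ivacaftor is twice the placebo rate and that washout events occur at the placebo rate. Write P(x) = 1 − exp(−x).

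- On-treatment window only: difference = P(2a) − P(a).
- As planned: ivacaftor = ½[P(2.5a) + P(2a)]; placebo = ½[P(1.5a) + P(a)].

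| a | On-treatment difference | Ivacaftor as planned | Placebo as planned | Planned difference | Loss, points |
|---|---|---|---|---|---|
| 0.1 | 8.6 | 20.1% | 11.7% | 8.4 | 0.2 |
| 0.5 | 23.9 | 67.3% | 46.1% | 21.2 | 2.6 |
| 1 | 23.3 | 89.1% | 70.4% | 18.7 | 4.6 |
| 2 | 11.7 | 98.7% | 90.7% | 8.0 | 3.7 |

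Over 0.5 to 2 events per 56 days the loss is about 3 to 5 points. At 0.1, nearer to a single preferred term, it is negligible. The direction of the difference is preserved throughout.

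**The case against.** The strongest reply is that the crossover balances the windows. Allocation is 1:1, each treatment gets both windows, and with equal complete sequences the false gap is exactly zero. This stands. A reader might infer that the rule tilts the safety comparison for or against ivacaftor; the documents do not support that, and they report no sequence imbalance or differential loss. If the trial held about 10 children, all treated in both periods (the documents give no final number), one child would be 10 points, so a false gap of 2 to 6 points is less than one child. Balance does not remove the attenuation.

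The asymmetry also has a reason. Children who continue to Part 2 start open-label ivacaftor at Week 24, so no off-drug tail can exist for them. A tail after Period 1 keeps delayed and withdrawal events with the drug that preceded them. That is a legitimate choice and argues for keeping that table. It does not argue against showing an equal-window one beside it.

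A reader might say that SAP 9.4.1 contradicts the protocol's rule of attribution by treatment at onset. That goes too far. Protocol 12.3.5.1 itself runs to the Safety Follow-up Visit, about four weeks after the last dose, for children who discontinue during a period. For completers it names no treatment for washout-onset events. The SAP can be read as filling that gap.

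SAP 9.4's mention of each applicable treatment period might mean by-period tables, in which completers on the two treatments would have equal windows. The wording could equally describe only the analysis population, and no by-period adverse event table is stated. It needs clarifying. All events are also listed by subject, so washout-onset events could be found in a small trial.

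**Conclusion.** The asymmetry is real but modest. For completers, the Period 1 treatment is charged with events over about 84 days, 28 of them off drug, and the Period 2 treatment over about 56, in tables with no adjustment for time at risk. Children who discontinue in Period 2 differ, because their window can run on to the Safety Follow-up Visit. The window lengths rest on the definitions in SAP 9.1, to which 9.4.1 refers; the general TEAE definition in 9.4.1 is broader and does not set them.

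The sizes found above rest on constant event rates, a washout rate equal to placebo, a rate ratio of 2 for the attenuation, and illustrative sequence splits, none of which the documents give.

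Two further inferences should not be drawn. On event counts, a true rate ratio of 2 would appear as (56×2 + 28 + 56×2)/(84 + 56) = 252/140 = 1.8, but the SAP tables count each subject once and do not report that ratio. And SAP 9.2.5, where "The duration will be calculated for the treatment corresponding to each treatment period", measures first to last dose and omits the tail. Dividing adverse event counts by it would mislead, but no planned analysis does so.

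Because safety is descriptive and no test or decision rule uses these tables, this is an improvement to consider. It does not invalidate the safety analysis.

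**What to change.** In SAP 9.4.1, keep the 28-day attribution table if wanted and add one ivacaftor-versus-placebo TEAE summary with the same on-treatment window in both periods: first dose through the Week 8 visit in Period 1, and first dose through the Week 24 visit, before any open-label dose, in Period 2. Show washout-onset events in a separate column, labelled by the preceding treatment, so that none is lost. State in SAP 9.4 whether by-period adverse event tables are intended. If event rates are ever added, use days in the treatment-emergent window as the denominator.

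The cost is a few lines of SAP text and one extra table or column from dates already collected. The drawback is that the on-treatment table holds slightly fewer events than the 28-day one.

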#### **9.4.2 Clinical Laboratory**

The following analyses for the lab assessments will be presented:

- Post-baseline values and change from baseline for chemistry, hematology, and LFT results will be summarized using SI units by treatment group at each scheduled time point.
- Abnormal hematology, chemistry, and LFT results will be summarized at each visit and also listed. Both abnormal low and high will be presented for hematology and chemistry results. Only abnormal high (elevated LFT) will be presented for LFT results.
- Number and percentage of subjects with abnormal LFT results meeting the threshold criteria will be summarized by treatment group at each scheduled time point. The threshold criteria for abnormal are provided in Appendix E. Results will also be presented overall by treatment group.
- The shift incidence of LFT results meeting threshold criteria against the baseline threshold criteria will be summarized by treatment group at each scheduled time point (only shifts to values worse than baseline will be presented).
- Box plots for the Ratio of LFT results to the ULN will be plotted against visit for each treatment group.
- Mean values ( $\pm$ SD) will be plotted against visit for ALT, AST, ALP, total bilirubin, and GGT for each treatment group.
- A scatterplot based on multiples of ULN will be provided for peak ALT versus peak total bilirubin and peak AST versus peak total bilirubin during the TE Period for each treatment group.
- Results of urinalysis and coagulation studies (only collected at screening) will be listed in individual subject data listings.

LFT includes ALT, AST, ALP, total bilirubin, and GGT. When presenting data for ALT and AST and additional category for ALT/AST (ALT or AST) will be presented.

Threshold analysis criteria for LFTs are presented in Appendix E.

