#### **12.3.5.2 Clinical Laboratory Assessments**

All statistical analyses of laboratory values will be performed using SI units. Continuous chemistry, hematology, and coagulation results will be summarized by treatment at each visit. Changes from baseline will also be summarized. The number and percentage of subjects with shift changes from baseline based on the laboratory normal ranges will be tabulated. The maximum on-treatment results will be tabulated by treatment and study part.

Urinalysis results will be listed but not summarized. In addition, a listing containing individual subject hematology, chemistry, and coagulation values outside the reference ranges will be provided. This listing will include data from scheduled and unscheduled time points.

Clinically significant abnormal findings will be reported as AEs.

Summary and analysis of elevation of LFT parameters will be provided in detail in the SAP.

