**Data Presentation:**

Where applicable and possible, data will be presented by ivacaftor dose group (50mg, 75mg and 150mg), placebo and overall ivacaftor dose group. For summary statistics, descriptive statistics will be presented for each visit and change from period baseline.

**Unscheduled Visits:** Unscheduled visit measurements will be included in the following:

- derivations of measurements at scheduled visits per specified visit windowing rules;
- derivations of baseline/last on-treatment measurements;
- derivations of the maximum/minimum on-treatment values and maximum/minimum changes from baseline values for safety analyses;
- data listings where appropriate.

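### SAP 9.4.2 omits, without declaring it, the chemistry and hematology shift and maximum on-treatment tables that Protocol 12.3.5.2 requires; LFTs are not affected

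*SAP*

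**What the plan says.** Protocol 12.3.5.2, in the paragraph on chemistry, hematology and coagulation, asks for two categorical or extreme-value outputs. The first is a shift table: "The number and percentage of subjects with shift changes from baseline based on the laboratory normal ranges will be tabulated". The second output concerns the most extreme value reached by each child on treatment: "The maximum on-treatment results will be tabulated by treatment and study part". The same section also asks for a listing of out-of-range values, and says of it: "This listing will include data from scheduled and unscheduled time points".

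SAP 9.4.2 gives non-LFT chemistry and hematology summaries of values and of change from baseline. On abnormal results it says: "Abnormal hematology, chemistry, and LFT results will be summarized at each visit and also listed". Its only shift table is for LFTs: "The shift incidence of LFT results meeting threshold criteria against the baseline threshold criteria will be summarized by treatment group". The threshold counts and the peak-value scatterplots in that section are also for LFTs, defined there as ALT, AST, ALP, total bilirubin and GGT.

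SAP 9.1 (Visit Windowing Rules) keeps, for safety parameters, the record nearest the target day, "with the exception of the threshold analysis in which the worst record will be used". SAP 9.1 (Unscheduled Visits) says that unscheduled samples enter "derivations of the maximum/minimum on-treatment values and maximum/minimum changes from baseline values for safety analyses". SAP 3.1 states that nothing was changed from Protocol Version 4.0.

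**The concern.** Clinical laboratory values are part of the Part 1 safety endpoint. A shift table shows how many children who started in range left it on each treatment. A maximum on-treatment table shows the most extreme value, whenever it was taken. For non-LFT chemistry and hematology the SAP names neither.

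The by-visit abnormality table replaces neither. It counts a long-standing abnormality and a new one alike, and it depends on a windowing rule that favours the scheduled end-of-period sample. Protocol 11.5.2 (Additional Evaluations) allows extra laboratory tests when clinically appropriate, so an unscheduled sample may be an informative one.

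The omission is also undeclared. Protocol Version 4.0 already reflects early termination and reduces other analyses because of low numbers (12.3.3.1, 12.3.3.2), yet it keeps both laboratory tables. A reader relying on SAP 3.1 would expect to find them.

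**Working it through.** The plan states no figure on this point, so the check compares outputs and then applies the windowing rule.

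**1. Outputs side by side (non-LFT chemistry and hematology)**

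| Output | Protocol 12.3.5.2 | SAP 9.4.2 |
|---|---|---|
| Values and change from baseline by visit | required | kept |
| Shift on normal ranges | required | LFTs only, on threshold criteria |
| Maximum on-treatment | required, by treatment and study part | none (peak plots for ALT, AST and bilirubin only) |
| Abnormal results by visit | not named | added |
| Out-of-range listing | required | kept |

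Coagulation is collected at Screening only (Protocol Table 11-1), so nothing is lost there.

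**2. Which record enters the by-visit table**

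Inputs:
- Appendix C, laboratory rows: one post-baseline visit per period, target Day 57. The window is Days 2 to 85 in Period 1, and Day 2 to the Week 24 visit date in Period 2.
- SAP 9.1: the closest record wins; at equal distance the latest wins.
- Protocol Table 3-2: Week 8 and Week 24 visits ± 5 days.
- Assumption: the scheduled sample exists and falls on Days 52 to 62.

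Period 1:
- Window length: 85 − 2 + 1 = 84 days.
- Days within 5 of the target: 62 − 52 + 1 = 11.
- Days always farther from the target than the scheduled sample: 84 − 11 = 73 (Days 2 to 51 and 63 to 85). 73/84 = 86.9%.

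Of the 83 other days in the window, the number on which an unscheduled sample loses depends on the scheduled day:

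| Scheduled sample | Losing days |
|---|---|
| Day 52 | 73 |
| Day 57 | 83 |
| Day 62 | 74 (Day 52 ties and loses as the earlier record) |

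Period 2: by the same rule, an unscheduled sample on Days 2 to 51 always loses.

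So an abnormal Day 30 sample is replaced in the table by a normal Week 8 sample. The worst-record exception does not help, because SAP 9.4.2 specifies a threshold analysis only for LFTs.

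**3. What a by-visit count can show about new abnormalities**

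With n children, b abnormal at baseline and w at Week 8, the number newly abnormal can lie anywhere from max(0, w − b) to min(w, n − b). For an assumed n = 10 and b = w = 3 (no document gives these values), the range is 0 to 3 of the 7 initially normal children, or 0% to 43%. The example shows only that the margins do not determine the shift; it does not estimate an effect.

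**The case against.** **The adverse event route.** Protocol 11.5.2 requires clinically significant abnormal results to be reported as AEs. Protocol 13.1.1.2 counts a result as clinically significant if it comes with related signs or symptoms, leads to further diagnostic tests or intervention, or changes study drug or participation. SAP 9.4.1 then separates pre-treatment from treatment-emergent events, attributes them by period and tabulates them, whatever the visit window. This stands. It covers many of the unscheduled samples that matter most.

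**LFTs.** These are the only laboratory tests with interruption or discontinuation limits in the protocol, and they keep threshold counts by visit and overall, the worst-record rule, a shift table and peak plots. This stands, and the point excludes them.

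**Appendix E.** It lists chemistry and hematology bands as threshold criteria. If the abnormality summary were meant to use them, the worst record would apply and the windowing point would fall. But SAP 9.4.2 cites Appendix E only for LFTs. Appendix E also includes tests absent from Protocol Table 11-1 (cholesterol, triglycerides, magnesium), so a band there does not show that an analysis is planned. Even on this reading, the missing baseline cross-classification and the undeclared omission remain.

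**Listings and small numbers.** In a small descriptive analysis, listings let a reader trace each child. This stands and lowers the priority.

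A reader might infer that new laboratory abnormalities on ivacaftor would be hidden, or that the safety tables would wrongly show no difference from placebo. The documents do not support that, given the AE tables, the LFT displays and the listings. Nor is 87% a share of samples lost: it is a share of calendar days, and the documents do not say how many unscheduled samples exist.

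**Conclusion.** The point holds for non-LFT chemistry and hematology, as a low-priority misalignment between protocol and SAP. Two required tables are absent and SAP 3.1 does not say so. The substitute table cannot separate new from existing abnormality and, when a Week 8 sample exists within its visit tolerance, it excludes unscheduled samples on 73 of 84 Period 1 window days. If the scheduled sample is missing, an unscheduled one can enter.

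What the tables can miss is mainly new abnormalities that the investigator did not judge clinically significant. The conclusion assumes that SAP 9.4.2 names every laboratory table planned. The on-treatment maxima and minima derived in SAP 9.1 suggest an incomplete specification rather than a reasoned decision to drop the tables.

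**What to change.** In SAP 9.4.2, add for Part 1, by treatment, for chemistry and hematology tests that Protocol Table 11-1 collects after Screening:

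1. A shift table: period-baseline category (low, normal, high) against the worst on-treatment category in that period, unscheduled samples included. Say how a child with both low and high values in a period is counted, for example with separate shifts to low and to high.
2. A table of maximum and minimum on-treatment values, using the derivations already in SAP 9.1.

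Restricting this to Part 1 fits SAP 4 and 9.4, which base the final analysis mainly on Part 1. Use of the Appendix E bands is optional, because the protocol asks only for shifts on normal ranges. If the sponsor prefers not to produce the tables, SAP 3.1 should record the omission and the reason.

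The cost is a few extra tables from data already collected. Cell counts will be small, so the tables should be read with the listings.
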